Evaluation of MyoStrain™ in Clinical Practice

December 4, 2018

Investigators

[name] (PI), [name] (sub-investigator), [name] (study coordinator), [name] (study coordinator), [name], MS (study coordinator), [name] (study coordinator), [name], MS (study coordinator), [name] (study coordinator), [name] (MRI technologist), Department of Radiology, [name], (sub-investigator), Department of Cardiology

Purpose of Project

This study is designed to evaluate the use of MyoStrain cardiac MRI (CMR) pulse sequence to determine how the use of this single pulse sequence may alter treatment decisions and clinical outcomes in patients who are undergoing cardiac MRI. Strain Encoding (SENC) MRI technology is a rapid MRI scan providing detailed structural and functional imaging of the heart muscle, and is of great diagnostic value in guiding treatment decisions for patients with heart failure, drug toxicity (e.g. chemotherapy), and coronary artery disease. The goal is to determine if Myostrain CMR can detect subtle changes of heart damage earlier or with more sensitivity/specificity to ultimately improve patient outcomes and earlier intervention in their treatment course. The purpose is to determine if and how patients treatments are impacted (morbidity/mortality outcomes) as a result of using this SENC sequence, or if there is no significant difference between the current gold standard (regular cardiac MRI, ultrasound, or nuclear medicine heart scans).

Specific Objectives

- The primary objective is to evaluate the workflow for rapid MyoStrain testing in clinical practice, and its direct clinical impact in impacting clinical outcomes and changing therapeutic decision making by the treating physicians.
- The primary efficacy endpoint is the efficiency and accuracy of MyoStrain testing in obtaining global and segmental strain measurements including Global Circumferential Strain, Global Longitudinal Strain, Left Ventricular Ejection Fraction (LVEF), Mass, and Volumes. The workflow analysis will be performed by the investigators based on clinical experience compared to alternative imaging modalities.
- An additional primary efficacy endpoint will determine (quantitatively) the ability of Myostrain to influence treatment decisions by earlier detection of progressive heart disease when compared to the current gold standards.

Rationale/Background

Device Description

The MyoStrain SENC CMR Imaging System is limited to observational evaluation within the United States. The MyoStrain system has European approval with an EC Certificate according to Directive 93/42/EEC on Medical Devices, Annex II excluding Section 4 (CE 657862) in respect of: Design, development and manufacture of software for the quantification of cardiac MRI images.

Strain Encoding (SENC) MRI technology is a fast MRI scanning diagnostic test that measures the contraction of the heart muscle in one to three heartbeat(s) per image plane, depending on the specific pulse sequence and associated MRI Manufacturer Scanner type and software version. This means that patients can be scanned very fast, in many cases while breathing, and a complete view of the ventricles' health can be obtained in less than a minute. Quantitative assessment of the strength of the heart muscle can have many clinical applications, but its highest value is in the two largest heart disease populations: those patients with heart failure and coronary artery disease.

SENC is an MRI Pulse Sequence for Strain Encoding

- A pulse sequence is an algorithm that instructs the MRI scanner to acquire certain types of images. Any MRI scanner has a large number of pulse sequences for general and specialized imaging of different parts of the body. They produce images that show different anatomies, physiologies, or pathologies of the different tissues of the body. For imaging the heart, there is a group of specialized pulse sequences that can show different aspects of the heart, including, but not limited to, the structure of the heart, the motion of the heart, the tissue characterization of the muscle, the flow of the blood, the structure of the vessels, and more.
- The Strain Encoding (SENC) pulse sequence is a specialized pulse sequence that produces images of the heart muscle that reveal the underlying contraction of the muscle of a healthy heart and associated weaknesses in case of disease. The measurements of the deformations of regions within the heart muscle ("myocardium") associated by contraction and relaxation during a single heartbeat is measured by the mechanical quantity called "strain."
- Myocardial Solutions, Inc. software measures tissue deformation or "strain" from the pulse sequence images. Quantitatively, "strain" is a mechanical property of deforming objects and measured as the percentile change in spacing between two points on a deforming object. For example, when muscle contracts, the muscle length is shortened. For example, a 30% shortening of the muscle is measured as strain of negative 30%.
- Measuring the shortening of the Heart Muscle results in two parameters that SENC quantifies: circumferential and longitudinal strain. Strain measurement depends on "direction" of measuring. For measuring the contraction of the heart muscle, there are two main directions that are typically used: 1) longitudinal strain, which describes the contraction of the myocardium that contributes to the base-to-apex contraction of the heart chambers; 2) circumferential strain, which describes the contraction of heart muscle fibers around the circumference of the chambers of the heart.

- Using SENC, circumferential and longitudinal strain values in 37 regions are measured in less than 2 minutes.

The Intended Use of the MyoStrain SENC MRI acquisition is:

- MyoStrain SENC software receives image data from MRI storage archives and performs viewing, image manipulation, communication, printing, and quantification of images. Available measurements include longitudinal and circumferential strain to quantitatively describe the wall motion of the heart. Tools are provided for display of regional motion properties of the heart.
- This unique sequence (SENC) will be used as an add-on to already-ordered cardiac MRI in many clinical scenarios (heart-failure, chemotherapy-related heart toxicity, inflammatory conditions such as sarcoid) to detect earlier progression or new heart-disease, that will change the management of patients (e.g. decreasing the amount of chemotherapy, changing chemotherapy regimen, or adding new cardiac failure drugs to prevent further decline or improve heart function).
- A report interface is provided. Measurement tools provide information that can be output in standardized or specialized report formats. This interface makes it possible to quickly and reliably fill out a complete clinical report of a cardiac imaging exam with strain. The results of the measurement tools are interpreted by the physician and can be communicated to referring physicians to support the determination of a diagnosis.

Clinical & Preclinical Testing

Myocardial Solutions, Inc. (MSI) SENC Software was implemented with SENC MRI acquisition using source codes that were developed at Johns Hopkins University. Both Diagnosoft before and MSI today continue to use the original SENC strain source code. SENC pulse sequences, derived from the SENC source code, designed for Philips, Siemens, and GE MRI Scanners, have been validated with phantom models, and clinical testing.

The MSI software leverages prior SENC image acquisition and processing functions that have been extensively studied on volunteers, phantoms studies, and clinical applications. The Fast SENC software processes images obtained with the well-studied SENC pulse sequence, which has supported several publications demonstrating the utility of strain imaging for various clinical applications.

Implementation of the SENC MRI acquisition in the Myocardial Solutions SENC Software has been validated as evidenced by literature across three separate comparisons: Comparisons with 1) Diagnosoft HARP, a 510k FDA certified software for measuring strain from tagged MR images; 2) EchoPAC STE, a certified software from GE Vingmed for measuring strain using speckle tracking methods; and 3) various physiological and pathological indicators.

Validation of SENC relative to Diagnosoft HARP

- Diagnosoft HARP is a 510k certified software for the analysis of MR Tagging images of the heart and measuring the strain that reveals the deformation of the myocardium as the heart muscle contracts and relaxes. Diagnosoft HARP is considered to be the gold standard for measuring regional strain and there are over 100 peer-reviewed published studies on the use of strain from HARP.
- Published Comparisons: SENC versus Diagnosoft HARP compared the strain measurements from SENC to strain calculated by MR Tagging and Diagnosoft HARP software. [1] [2] [3] The comparisons showed strong correlation in measurements of strain, both regional and global, and also the different strain measurements, such as longitudinal and circumferential strain; the correlation between SENC and tagged MRI was significant with $R=0.90$.
- The published literature demonstrates that SENC strain measurements are comparable to those obtained used MR Tagging and HARP software, which is the gold standard method for measuring strain.

Comparison of SENC to EchoPAC, GE Vingmed STE

- EchoPAC is a 510k and CE Mark certified package form GE Vingmed for the processing of echocardiographic images and films. It can measure the deformation and strain of tissue using speckle tracking echocardiography (STE), which is an image post-processing algorithm.
- Published Comparisons: SENC versus EchoPAC STE compares the strain measurements from SENC to the strain calculated using Tissue Strain Echocardiography (STE). [4] STE was calculated using EchoPAC software from GE.
- Cardiac MRI measurements of strain using SENC and MR tagging are considered to be equivalent to STE or better due to the excellent image of cardiac tissue by MRI and creation of actual physical markers inside the tissue to measure strain. STE is an image processing method that tries to extract motion and strain from conventional echocardiographic movies with their known image quality limitations.
- The published comparisons showed a correlation between strain measurements obtained by SENC and those calculated by STE. It is important to point out that MRI, as a gold standard method, was used as the reference for measuring strain. STE post-processing calculations were expected to be inherently inferior as it inherits some of the suboptimal image qualities of echocardiography (relative to MRI).

Validation of SENC MyoStrain Based on Clinical Physiological and Pathological Indicators

- SENC strain was directly compared to different physiological and pathological indicators to understand the mechanics of the heart muscle and alterations due to underlying disease and pathology. This includes the understanding of the contraction of the left and right ventricles, changes in strain in the case of myocardial infarction as determined using delayed enhancement methods, and detection of ischemia in patients by utilizing stress testing.

- Published Comparisons: SENC Strain for Physiological and Pathological Indicators. Different studies were done using SENC to understand the mechanics of the heart wall muscle and the changes that accompany certain diseases. In the case of coronary artery diseases, the studies showed changes in strain because of acute coronary artery syndrome that results in myocardial infarction. Strain also detected ischemia when combined with stress, detecting ischemia at lower stress levels compared to stress CINE MRI.
- Stress testing for ischemia, performed on patients with suspected or known ischemic heart disease, demonstrated that measured strain was more sensitive in detecting stenosis in the coronary arteries compared to 1) conventional cine movies with qualitative assessment of abnormal wall motion under stress, and 2) the outcomes of revascularization of positively diagnosed patients. [5] [6] [7] [8] [9]
- Myocardial infarction studies show the value of strain measurements in assessing, with high accuracy, changes in regional function associated with damage from myocardial infarction. [10] [11] [12] [13] Quantification of changes in contraction is more accurate (more sensitive and specific) in associating with the depth of damage vis-à-vis subjective wall motion assessment.
- Cardiac mechanics studies illustrated other applications of SENC strain measurements in understanding the mechanics of the heart, especially the left and right ventricles. [14] [15] [16] [17] [18] These healthy subjects studies demonstrated, with high accuracy and precision, the ability to detect subtle variations in regional contraction. Also, quantification revealed variations in contractility as a result of diseases affecting the right ventricle, which is very hard to assess using echocardiography because of the position of the right ventricle close to the ribs and the sternum and its geometry.

Methodology

This prospective study will include up to 100 patients who will be enrolled based on meeting the stated inclusion/exclusion criteria. Upon completion of the informed consent, patients will undergo SENC MyoStrain testing in a Siemens Manufacturer Scanner with a validated pulse sequence. The testing will incorporate baseline MyoStrain Testing in which 3 short axis slices and 3 long axis slices will be planned for imaging and then recorded with MyoStrain testing.

System setup and testing methodology will follow the Myocardial Solutions SENC User's Manual 4.x. The SENC MyoStrain Test procedure is a quick and simple analysis which will require only one series of images. The importation of the images from the scanner and organization of these images is mostly automated and requires very minimal interaction to function correctly. The workflow of the SENC MyoStrain test requires only one scan and analysis phase allowing the complete scan to be completed within 2 minutes after imaging planning.

Data obtained for the clinical and research scan will be stored in PACS. KUMC will provide the first 20 de-identified MyoStrain raw images and outcome reports to MyoCardial Solutions.

Inclusion Criteria

- Patients already scheduled for diagnostic testing with commercially available imaging modality (cardiac MRI)
- The patient population will include (but not limited to), those being evaluated for heart disease and heart failure that may be related to vascular disease (coronary artery disease), drug related heart failure (chemotherapy, alcohol), inflammatory systemic conditions (sarcoidosis, amyloidosis, lupus), myocarditis, and/or infectious etiologies
- Provided written informed consent

Exclusion Criteria

- Contraindication to Magnetic Resonance Imaging

Risks

The SENC MyoStrain software with the associated MRI Manufacturer Scanner pulse sequence is a noninvasive imaging technology. There is minimal direct physical risk for imaged subjects as it is an MRI procedure that does not require any invasive intervention or injections. As such the risks are limited to those typical for conventional non-contrast (e.g. without contrast injection) MRI exams. Subjects will be evaluated as an inclusion criteria for potential contraindications to MRI imaging. Considering image acquisition is very fast (< 5 min) reducing time within the magnetic bore, risks of claustrophobia or anxiety may be reduced compared to traditional MRI tests.

The MSI SENC MyoStrain software has been tested and validated following ISO 14971 (Medical Devices – Application of Risk Management to Medical Devices).

Detailed risk assessments have been done by Myocardial Solutions, Inc. throughout the software development. The company routinely performs management review that include analysis of device performance, change control (design, process, labeling), and corrective and preventative action for the product.

Myocardial Solutions' risk assessment has been completed and clinical risks have been reduced as far as possible by device design, labeling, and training protocols for intended users. There are no unacceptable residual clinical risks based on the risk/benefit reviews.

Data Management

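### The primary objective and purpose include SENC's effect on clinical outcomes, but no outcome endpoint, outcome follow-up or group managed without the SENC result is described

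*Protocol*

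**What the plan says.** Under Specific Objectives, the primary objective is to evaluate the workflow of rapid testing and "its direct clinical impact in impacting clinical outcomes and changing therapeutic decision making by the treating physicians". Outcomes and treatment decisions are named there as two separate things.

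Purpose of Project makes the same pairing. The study is to determine "how the use of this single pulse sequence may alter treatment decisions and clinical outcomes in patients who are undergoing cardiac MRI", and a later sentence says it will "determine if and how patients treatments are impacted (morbidity/mortality outcomes) as a result of using this SENC sequence, or if there is no significant difference". That sentence goes on to name the current gold standard, which it lists as regular cardiac MRI, ultrasound or nuclear heart scans.

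Two primary efficacy endpoints follow:
- "The primary efficacy endpoint is the efficiency and accuracy of MyoStrain testing in obtaining global and segmental strain measurements", together with LVEF, mass and volumes.
- "An additional primary efficacy endpoint will determine (quantitatively) the ability of Myostrain to influence treatment decisions by earlier detection of progressive heart disease", judged against the current gold standards.

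On design, the intended-use list under Rationale/Background says "This unique sequence (SENC) will be used as an add-on to already-ordered cardiac MRI in many clinical scenarios". Methodology says "This prospective study will include up to 100 patients who will be enrolled based on meeting the stated inclusion/exclusion criteria", that consented patients undergo SENC, and that "The testing will incorporate baseline MyoStrain Testing in which 3 short axis slices and 3 long axis slices will be planned for imaging". Data Management covers storage of scan data and the sending of images and reports to the company.

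**The concern.** An objective, its endpoints and the design should answer the same question. Here the primary objective asks what SENC does to clinical outcomes, and the purpose attributes morbidity and mortality effects to its use. The endpoints listed beneath that objective measure something else.

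If the wording stands, the study could be reported as having evaluated SENC's effect on morbidity or mortality, favourably or as no effect, when what it gathered was measurements and, at most, treatment decisions. A change in a treatment decision is not evidence that the patient did better or worse, and the protocol itself keeps the two apart.

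**Working it through.** The main check is a comparison of sections and needs no formula. The protocol gives no derivation of its ceiling of 100 patients (no event rate, effect size, power or follow-up time), so there is no stated calculation to reproduce.

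**1. What an outcome conclusion needs, and what the protocol describes**

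| Requirement | Where to look | What is described |
|---|---|---|
| A clinical outcome among the primary endpoints | Specific Objectives | 0 of 2: measurement performance, and treatment decisions |
| Patients managed without the SENC result | Intended-use list, Methodology | None: SENC is an add-on for every consented patient |
| Outcome follow-up after the scan | Methodology, Data Management | No visit, duration or time point |
| Collection of clinical events | Data Management | None: scan data go to PACS |

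**2. Items that might be mistaken for outcome data**

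- Methodology and Data Management mention outcome reports. These go to the company with the first 20 raw image sets, and Data Management gives the reason as quality control and certifying technologists. They are not patient follow-up.
- Up to five scans may be requested each quarter. The stated reason is technologist proficiency, not reassessment of patients.

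**3. What the named comparators can do**

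The comparators are imaging modalities: routine cardiac MRI, ultrasound and nuclear scans. Setting SENC beside another modality can bear on accuracy, or on whether a decision would differ. It does not show how the patient would have fared had the SENC result not been available, because every patient has it.

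**4. Whether sample size is the issue**

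It is not. With no outcome endpoint, no follow-up and no contrast between patients with and without SENC, no number of patients answers the outcome question.

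For the separate question of whether a comparison group could fit within 100 patients, take the usual two-proportion formula, two-sided 5% and 80% power, with control rate p, q = p/2 and m = (p+q)/2:

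n per group = [1.960·√(2m(1−m)) + 0.8416·√(p(1−p)+q(1−q))]² / (p−q)²

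- p = 0.20, q = 0.10, m = 0.15: (0.990 + 0.421)² / 0.01 ≈ 199 per group, 398 in total.
- p = 0.60, q = 0.30, m = 0.45: (1.379 + 0.565)² / 0.09 ≈ 42 per group, 84 in total.

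Both rates, and the halving, are assumptions. One total exceeds 100 and the other does not, so the documents settle nothing on this question.

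**The case against.** **The study has comparators.** This is correct, and it limits the point. Purpose of Project and Specific Objectives name other modalities, and the already-ordered cardiac MRI may give a within-patient reference. A reader might infer that nothing is compared at all; the text does not support that. What is missing is a group managed without the SENC result, and that is what an outcome conclusion would need.

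**The no-significant-difference wording concerns modalities.** Read in full, the sentence sets SENC against the gold-standard scans, and its grammatical subject is the patients' treatments. A reader might infer that the protocol plans to declare no difference in outcomes. The sentence is ambiguous, and that reading is not established. It calls for a clarification only.

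**Later scans are not ruled out.** This also stands. The remark about a single scan and analysis phase describes how the test is run, and the word baseline does not say that nothing follows. A reader might infer exactly one scan per patient; the safe statement is that no later scan is described. Repeat scans would in any case supply neither clinical events nor patients managed without SENC.

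**An outcome comparison might fit in 100 patients.** It might, at high enough event rates, as the second calculation shows. A reader might infer that the ceiling rules out a comparison group, but that depends wholly on rates the protocol does not give.

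**The SAP may cover it.** A SAP analyses what the protocol collects. It cannot supply a comparison group, follow-up or event collection.

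**The endpoints are explicit, so nobody will be misled.** This reduces the harm but does not remove the mismatch. The goal of ultimately improving patient outcomes can be read as aspiration; a stated primary objective cannot.

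**Conclusion.** The mismatch is real and sits inside the protocol. The outcome part of the primary objective and purpose has no endpoint (0 of 2), no described follow-up, no described event collection and no described patients managed without the SENC result. The design cannot support a conclusion in either direction about SENC's effect on morbidity or mortality.

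This rests only on what the protocol describes, with no assumed event rate. It does not impugn the two stated endpoints, which a comparison of modalities may serve. The wording should be corrected, because it governs what the study may claim.

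**What to change.** Align the wording with the two endpoints.

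- **Primary objective.** Restate it along these lines: *to evaluate the workflow, efficiency and accuracy of rapid MyoStrain testing in practice, and its influence on the treating physicians' decisions through earlier detection of progressive heart disease than with the current gold standards.* This keeps both endpoints whole.
- **Purpose.** Delete the reference to clinical outcomes in the opening sentence and the parenthesis on morbidity and mortality. Mark the goal of ultimately improving patient outcomes as a long-term rationale that this study does not test.
- **No significant difference.** State that any such conclusion concerns imaging modalities or treatment decisions, not outcomes.
- **If outcomes are reported at all.** Label them descriptive and state that no effect of SENC on clinical outcomes will be claimed.

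The cost is a more modest stated aim. No patients, scans or visits are added, and the ceiling of 100 stays. How the influence on treatment decisions is to be recorded is a separate matter.

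### The workflow item of the primary objective is to be judged from investigators' experience, with no variable that must be recorded and no single comparator chosen

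*Protocol*

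**What the plan says.** Under Specific Objectives, the protocol opens with workflow: "The primary objective is to evaluate the workflow for rapid MyoStrain testing in clinical practice". The next bullet, which defines the first primary efficacy endpoint as efficiency together with accuracy, closes with the only statement in the document on how workflow will be assessed: "The workflow analysis will be performed by the investigators based on clinical experience compared to alternative imaging modalities". The third bullet describes the other primary endpoint in different terms: "An additional primary efficacy endpoint will determine (quantitatively) the ability of Myostrain to influence treatment decisions".

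The possible comparators appear under Purpose of Project, as the "current gold standard (regular cardiac MRI, ultrasound, or nuclear medicine heart scans". That list is not tied to the workflow analysis. The intended-use part of the Device Description gives the place of the new sequence: "This unique sequence (SENC) will be used as an add-on to already-ordered cardiac MRI in many clinical scenarios". Inclusion Criteria require that the patient already be scheduled for a cardiac MRI.

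Methodology sets the size ("This prospective study will include up to 100 patients") and outlines the procedure: "3 short axis slices and 3 long axis slices will be planned for imaging and then recorded with MyoStrain testing". It adds: "The workflow of the SENC MyoStrain test requires only one scan and analysis phase". Data Management says that clinical and research scan data go to PACS. It does not mention timing or workflow data.

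**The concern.** A primary assessment needs something that is recorded in each patient and something to compare it with. For workflow, the protocol supplies neither. It names a source of judgement, the investigators' clinical experience, and a plural group of alternatives.

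Two investigators could follow the sentence faithfully and reach different answers, one thinking of echocardiography and the other of a standard cardiac MRI. Neither answer could be checked by a third person, because no data would lie behind it. If a comparison with ultrasound or nuclear imaging were made, it might have to draw on experience with other patients, since study patients need not have had those tests. What is at stake is whether the workflow conclusion can be reproduced and interpreted.

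**Working it through.** No arithmetic bears on the defect. The protocol gives no significance level, power, SD, margin or effect size for workflow, and the 100 patients are a ceiling without a derivation. The check is a reading of the whole document with three questions.

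**1. Is any workflow variable required?**
- Specific Objectives name strain, LVEF, mass and volumes. These are outputs of the test and bear on accuracy.
- Device Description, Methodology and Risks quote SENC times. They describe the device; none is set as an outcome to be recorded.
- Data Management covers storage of scan data, transfer of the first 20 de-identified image sets and reports, and up to five scans per quarter for technologist proficiency. No time, completion rate or rating scale is mentioned.

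Result: none is required. Equally, nothing forbids recording one.

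**2. Is a single comparator selected?**
- Purpose of Project lists three modalities joined by *or*. The workflow sentence refers to alternatives in the plural and picks none.
- Inclusion Criteria assure one modality for every patient, cardiac MRI, and SENC is added to that exam.

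Result: candidates are listed and one is the natural reference, but none is chosen. Within-study data on ultrasound and nuclear scans are not assured.

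**3. Could a later document repair this from stored data?**
- Acquisition: images are kept in PACS, so image times may be recoverable. That timestamps are usable is an assumption; the protocol does not say so.
- Planning: Methodology puts slice planning before the recording of images. The protocol provides no record of when it starts.
- Analysis: Methodology counts analysis as part of the workflow. No record of its duration is provided for either.

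Result: acquisition time might be recovered afterwards. Planning and analysis time cannot be relied on unless logged at the time.

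**The case against.** The strongest reply is that metrics, start and stop rules and intervals are operational detail for an SAP or a data form, and that the sentence does not exclude measurement. Much of that is fair: a protocol silent on the method would give no ground for this point. But this protocol states a method for the first item of its primary objective, and that method is experience. A later plan also could not restore planning or analysis times that nobody logged.

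Several stronger readings are tempting and are not supported:

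- *The whole first primary endpoint is a matter of impression.* Workflow and efficiency share a bullet but are not expressly equated. A separately measured efficiency endpoint remains an open reading, so the point is confined to workflow.
- *The comparator is entirely unspecified.* Three candidates are listed in Purpose of Project, and the add-on design points to the patient's own cardiac MRI. What is missing is the choice.
- *Workflow means added minutes.* Methodology also speaks of largely automated image import and little user interaction, and the intended-use text of reporting. Added time is one measurable part, and user experience is a legitimate way to describe ease of use.
- *The SENC times quoted across the protocol conflict.* They run from under one minute to under five, but they are compatible upper bounds on different steps and show no error.
- *The other primary endpoint shows how it should be done.* It is called quantitative, but it names no variable or single comparator either. The contrast is one of wording only.

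It is also true that this is an observational evaluation, and that no threshold, test or decision rule depends on the workflow result.

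**Conclusion.** The point holds in a limited form. The protocol fixes the workflow analysis as investigators' experience against alternatives that are not narrowed to one, and it requires no workflow quantity to be recorded. The result would be an impression that cannot be reproduced and may depend on the modality each investigator has in mind.

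No numerical harm can be derived from the document. Any precision in minutes would need an SD that the protocol does not give, so it is no evidence of a defect. Patient safety and the treatment-decision endpoint are not affected. The conclusion rests on reading the workflow sentence as the operative method, which is reasonable because it is the only one stated. The change should be made because it is cheap and because part of the data cannot be recovered later.

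**What to change.** Replace the workflow sentence in Specific Objectives with:

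> For each patient, the minutes SENC adds to the ordered cardiac MRI are recorded from start of SENC slice planning to the last SENC image, with SENC analysis minutes recorded separately. Image times come from stored image timestamps where available; planning and analysis times are logged prospectively. The patient's own clinical cardiac MRI is the reference, and the mean added time is reported with a 95% CI. Investigator impressions (ease of use, reporting) and comparisons with ultrasound or nuclear scans are descriptive.

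A paired comparison with the cine block of the clinical exam can be an option, but not the main measure. The protocol does not say that every clinical exam contains a separable cine block. Where one exists, the same start and stop rule should apply to both blocks, and the report should note that they may deliver different outputs.

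The cost is one rewritten passage, extraction of image times from scans already stored, and a short prospective log kept by staff. No extra scan, reader or patient is needed. The downside is the logging effort, and that workflow comparisons with ultrasound and nuclear imaging, which Purpose of Project names among the current standards, become descriptive only.
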